### **4.3. Withdrawal Criteria and Procedures**

A subject may withdraw from study treatment at any time at his/her own request, or may be withdrawn at any time at the discretion of the investigator for safety, behavioral or administrative reasons.

Should a subject fail to attend the clinic for a required study visit, the site should attempt to contact the subject and re-schedule the missed visit as soon as possible. The site should also counsel the subject on the importance of maintaining the assigned visit schedule and ascertain whether or not the subject wishes to and/or should continue in the study based on previous non-compliance. In cases where the subject does not return for the rescheduled visit or cannot be reached to reschedule the missed visit, the site should make every effort to regain contact with the subject (3 telephone calls and if necessary a certified letter to the subject's last known mailing address) so that they can appropriately be withdrawn from the study.

These contact attempts should be documented in the subject's medical record. Should the subject continue to be unreachable, then and only then will he/she be considered to have withdrawn from the study with a primary reason of "Lost to Follow-up". For all other subjects withdrawing from the study, an alternative reason for discontinuation should be recorded in the Case Report Form (CRF). If a subject prematurely withdraws from participation in the study for any reason, the investigator/sub-investigator must make every effort to assess the items specified on discontinuation test.

Refer to Section 5.2.1 for Liver Chemistry stopping criteria, Section 5.2.2 for QTc withdrawal and Section 7.2 for Pregnancy.

Liver chemistry threshold stopping criteria have been designed to assure subject safety and to evaluate liver event etiology (in alignment with the Food and Drug Administration [FDA] premarketing clinical liver safety guidance). See Section 5.2.1 for details.

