##### 5.2.1. Liver Chemistry Stopping Criteria

Liver chemistry threshold stopping criteria have been designed to assure subject safety and to evaluate liver event etiology (in alignment with the FDA premarketing clinical liver safety guidance).

Study treatment will be stopped **for a subject** if the following liver chemistry stopping criteria is met:

- ALT  $\geq 3 \times$ ULN

NOTE: Refer to [Appendix 1](#) for details of the required assessments if a subject meets the above criteria.

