### 6.2.1. Liver Chemistry Follow-up Procedures

**Liver chemistry withdrawal criteria** have been designed to assure subject safety and evaluate liver event etiology.

Liver chemistry stopping criteria 1-3 are defined below:

- 1 ALT  $\geq 3xULN$  **and** bilirubin  $\geq 2xULN$  (>35% direct bilirubin) (or ALT  $\geq 3xULN$  **and** international normalised ratio (INR) >1.5, if INR measure).

NOTE: if serum bilirubin fractionation is not immediately available, study drug should be discontinued if ALT  $\geq 3xULN$  and bilirubin  $\geq 2xULN$ . Serum bilirubin fractionation should be performed if testing is available. If testing is unavailable, **record presence of detectable urinary bilirubin on dipstick**, indicating direct bilirubin elevations and suggesting liver injury.

- 2 ALT  $\geq 5xULN$ .
- 3 ALT  $\geq 3xULN$  if associated with the appearance or worsening of symptoms of hepatitis or hypersensitivity such as fatigue, nausea, vomiting, right upper quadrant pain or tenderness, fever, rash or eosinophilia.

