**When any of the liver chemistry withdrawal criteria is met, do the following:**

- Report the event to GSK **within 24 hours** of learning its occurrence
- Complete the liver event CRF and SAE data collection tool if the event also meets the criteria for an SAE. All events of ALT  $\geq 3xULN$  **and** bilirubin  $\geq 2xULN$  (>35% direct bilirubin) (or ALT  $\geq 3xULN$  **and** INR >1.5, if INR measured; INR measurement is not required and the threshold value stated will not apply to patients receiving anticoagulants), termed 'Hy's Law', **must be reported as an SAE (excluding studies of hepatic impairment or cirrhosis)**.

NOTE: if serum bilirubin fractionation is not immediately available, study drug should be discontinued if ALT  $\geq 3 \times \text{ULN}$  **and** bilirubin  $\geq 2 \times \text{ULN}$ . Serum bilirubin fractionation should be performed if testing is available. If testing is unavailable, **record presence of detectable urinary bilirubin on dipstick**, indicating direct bilirubin elevations and suggesting liver injury.

- Complete the liver imaging and/or liver biopsy CRFs if these tests are performed
- Perform liver event follow up assessments, and monitor the subject until liver chemistries resolve, stabilize, or return to baseline values as described below.
- Withdraw the subject from the **study** (unless further safety follow up is required) after completion of the liver chemistry monitoring as described below.

In addition, for criterion 1:

- Make every reasonable attempt to have subjects return to clinic within **24 hours** for repeat liver chemistries, liver event follow up assessments (see below), and close monitoring
- A specialist or hepatology consultation is recommended
- Monitor subjects twice weekly until liver chemistries (ALT, AST, alkaline phosphatase, bilirubin) resolve, stabilize or return to within baseline values

For criteria 2 and 3:

- Make every reasonable attempt to have subjects return to clinic **within 24-72 hrs** for repeat liver chemistries and liver event follow up assessments (see below)
- Monitor subjects weekly until liver chemistries (ALT, AST, alkaline phosphatase, bilirubin) resolve, stabilize or return to within baseline values; criterion 5 subjects should be monitored as frequently as possible.

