- Subjects with ALT  $\geq 3 \times \text{ULN}$  **but**  $< 5 \times \text{ULN}$  **and** bilirubin  $< 2 \times \text{ULN}$ , without hepatitis symptoms or rash, and who can be monitored weekly for 4 weeks
- Notify the GSK medical monitor within 24 hours of learning of the abnormality to discuss subject safety.
- Must return weekly for repeat liver chemistries (ALT, AST, alkaline phosphatase, bilirubin) until they resolve, stabilize or return to within baseline
- If at any time these subjects meet the liver chemistry stopping criteria, proceed as described above
- If, after 4 weeks of monitoring, ALT  $< 3 \times \text{ULN}$  and bilirubin  $< 2 \times \text{ULN}$ , monitor subjects twice monthly until liver chemistries normalize or return to within baseline values.

For criteria 1-3, make every attempt to carry out the **liver event follow up assessments** described below:

- Viral hepatitis serology including:
  - Hepatitis A IgM antibody;
  - Hepatitis B surface antigen and Hepatitis B Core Antibody (IgM);
  - Hepatitis C ribonucleic acid (RNA);
  - Cytomegalovirus IgM antibody;
  - Epstein-Barr viral capsid antigen IgM antibody (or if unavailable, obtain heterophile antibody or monospot testing);
  - Hepatitis E IgM antibody
- Blood sample for pharmacokinetic (PK) analysis, obtained within one to two weeks after the liver event. Record the date/time of the PK blood sample draw and the date/time of the last dose of IP prior to blood sample draw on the CRF. If the date or time of the last dose is unclear, provide the subject's best approximation. If the date/time of the last dose cannot be approximated OR a PK sample cannot be collected in the time period indicated above, do not obtain a PK sample. Instructions for sample handling and shipping are in the SPM.
- Serum creatine phosphokinase (CPK) and lactate dehydrogenase (LDH).
- Fractionate bilirubin, if total bilirubin  $\geq 2xULN$
- Obtain complete blood count with differential to assess eosinophilia
- Record the appearance or worsening of clinical symptoms of hepatitis, or hypersensitivity, such as fatigue, nausea, vomiting, right upper quadrant pain or tenderness, fever rash or eosinophilia as relevant on the AE report form
- Record use of concomitant medications, acetaminophen, herbal remedies, other over the counter medications, or putative hepatotoxins, on the concomitant medications report form.
- Record alcohol use on the liver event alcohol intake case report form

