## 12. APPENDICES

### 12.1. Appendix 1: Liver Safety Process

The procedures listed below are to be followed if a subject meets the liver chemistry stopping criteria defined in Section 5.2.1:

- Notify the GSK medical monitor within 24 hours of learning of the abnormality to confirm the subject's study treatment cessation and follow-up.
- Complete the "Safety Follow-Up Procedures" listed below.
- Complete the liver event case report forms. If the event also meets the criteria of an SAE (see Section 7.1.3), the SAE data collection tool will be completed separately with the relevant details.
- Upon completion of the safety follow-up withdraw the subject from the study unless further safety follow up is required
- Do not restart study treatment
- Refer to the Flow chart for a visual presentation of the procedures listed below.

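### A symptom-free ALT of 3 to <5xULN after dosing leads to study withdrawal under Section 5.2.1 and Appendix 1 but only to monitoring under Section 6.2.1, and withdrawal can end PK and B-cell sampling

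*Protocol*

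**What the plan says.** **Route to withdrawal.** Protocol Section 4.3 directs the reader on withdrawal: "Refer to Section 5.2.1 for Liver Chemistry stopping criteria, Section 5.2.2 for QTc withdrawal and Section 7.2 for Pregnancy". Section 5.2.1 stops treatment "if the following liver chemistry stopping criteria is met" and lists one item, ALT of at least 3xULN, with no bilirubin or symptom condition. Appendix 1 applies to anyone meeting 5.2.1. It asks for medical-monitor notification within 24 hours, a work-up, the liver event form, and weekly chemistries until they resolve, stabilize or return to baseline. It then says: "Upon completion of the safety follow-up withdraw the subject from the study unless further safety follow up is required".

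**Route to monitoring.** Section 6.2.1 states: "Liver chemistry stopping criteria 1-3 are defined below". These are ALT at least 3xULN with bilirubin at least 2xULN (>35% direct) or INR >1.5; ALT at least 5xULN; and ALT at least 3xULN with hepatitis or hypersensitivity symptoms. Withdrawal is attached to these three. Subjects with ALT 3 to <5xULN and bilirubin <2xULN, "without hepatitis symptoms or rash, and who can be monitored weekly for 4 weeks", form a separate group. For them the instruction is "Notify the GSK medical monitor within 24 hours of learning of the abnormality to discuss subject safety", then weekly chemistries, then twice-monthly checks. Escalation is conditional: "If at any time these subjects meet the liver chemistry stopping criteria, proceed as described above".

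**What withdrawal stops.** Section 3.2 gives the single dose on Day 0. In Table 2 the PK and biological-marker rows run to Day 84, and both are blank in the discontinuation column. SAP 11.5.1 says that withdrawn subjects are not replaced and that their available planned data enter the summaries.

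**The concern.** The escalation sentence in 6.2.1 makes sense only if the monitoring group has not yet met the stopping criteria. Under 5.2.1 the same subject has already met them, so both texts cannot govern that subject. Table 4 does not settle it. Under a Phase III-IV heading, in a Phase I study, it waives the liver event form for this subject unless the elevation lasts 4 weeks or weekly monitoring is impossible, whereas Appendix 1 requires the form.

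Once the dose is in, stopping treatment has no content and study withdrawal is the only remaining effect. The cost falls on the primary endpoints: six of the seven PK parameters depend on the later samples, and only Cmax does not. B-cell follow-up, a secondary endpoint, would stop too. The exception in Appendix 1 is worded for safety follow-up and does not mention PK or PD visits. Appendix 1 does ask for one liver-event PK sample, but that does not replace the later scheduled ones.

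**Working it through.** **1. The plan's own figure.** Protocol 9.2.1 gives n = 12 and CV 32.1% for AUC(0-inf).
- Log SD = sqrt(ln(1 + 0.321²)) = 0.313.
- Half-width = exp(2.201 × 0.313/sqrt(12)) − 1 = 22.0%, as stated. The same formula with CV 20.0% gives the stated 13.4% for Cmax.

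**2. Scheduled samples lost.** These are the nominal sampling days later than (day the ALT rise is seen + time for liver tests to settle). Laboratory visits and sampling days come from Table 2. Settling time is not in the documents, so 1, 2, 4 and 8 weeks are shown.

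| ALT rise seen at | PK lost of 12 (1 / 2 / 4 / 8 weeks) | B-cell lost of 5 (1 / 2 / 4 / 8 weeks) |
|---|---|---|
| 24 h | 6 / 5 / 3 / 1 | 5 / 4 / 3 / 1 |
| Day 14 | 4 / 3 / 2 / 1 | 4 / 3 / 2 / 1 |
| Day 28 | 3 / 2 / 1 / 0 | 3 / 2 / 1 / 0 |
| Day 56 | 1 / 1 / 0 / 0 | 1 / 1 / 0 / 0 |
| Day 84 | 0 | 0 |

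**3. Share of AUC(0-inf) beyond the last sample.** Model: C = A·exp(−a·t) + B·exp(−b·t). Section 1.1.2 gives a terminal half-life of 19.4 days and a distribution half-life of 1.1-1.8 days, so b/a = 0.057-0.093. A/B is not in the documents; 0.5-2.5 is assumed.
- Share = 2^(−t/19.4) / (1 + (A/B)(b/a)). The denominator runs from 1 + 0.5 × 0.057 = 1.028 to 1 + 2.5 × 0.093 = 1.232.
- Day 14: 49-59%. Day 21: 38-46%. Day 28: 0.368/1.232 to 0.368/1.028 = 30-36%. Day 42: 18-22%. Day 56: 11-13%. Day 84: 4-5%.

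**4. Bias in AUC(0-t), last sample Day 28 against Day 84.**
- Lower end: 1 − (1 − 0.298)/(1 − 0.040) = 27%.
- Upper end: 1 − (1 − 0.358)/(1 − 0.048) = 32%.
- One such subject among 12 lowers the geometric mean by 1 − 0.731^(1/12) = 2.6% to 1 − 0.675^(1/12) = 3.2%.

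**5. Noise in one subject's log AUC(0-inf).** Simulation of 20,000 profiles per case, with 10% residual error assumed, log-trapezoid, and the tail taken as last observed concentration over lambda-z.

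| Last sample | Error SD, terminal fit from Day 7 | Error SD, terminal fit from Day 14 |
|---|---|---|
| Day 28 | 0.06-0.10 | 0.14-0.18 |
| Day 42 | 0.04-0.05 | 0.05-0.06 |
| Day 56 | about 0.04 | about 0.04 |
| Day 84 | 0.03 | 0.03 |

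**6. Effect on the primary summary.** One Day-28 profile among 12 gives log SD = sqrt(0.313² + e²/12), with e = 0.06 to 0.18, which is 0.314 to 0.317. The half-width becomes 22.1-22.3%, against 22.0%.

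**The case against.** The strongest reply is that this hardly matters. There is no hypothesis test, about 20 subjects are enrolled to obtain 12, and nine of 20 would have to be lost to fall below 12. If 20 are dosed and one is lost entirely, n = 19 gives a half-width of 16.3%, still inside 22.0%. Exclusion criterion 16 sets a 2xULN screening limit for AST and ALT, so the event generally needs a new rise (a 1.5-fold one from just under the limit). Withdrawal comes only after liver follow-up, which may run long enough to lose nothing. SAP 8.1.3 allows population PK modelling if data permit, and that can use truncated profiles. All of this stands and sets the size of the point. It does not remove the contradiction or the AUC(0-t) bias in an affected subject.

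Three stronger readings are tempting but not supported:
- **Unchecked divergence between sites.** In a multicenter study, two sites could act differently on the same result. But both routes bring in the sponsor's medical monitor within 24 hours, so divergence is possible, not uncontrolled.
- **A wrong flow chart.** The Appendix 1 diagram is missing from the text available here. Whether it agrees with either rule cannot be judged.
- **Withdrawal under criteria 1-3 is also an error.** There, 6.2.1 and Appendix 1 agree on withdrawal after follow-up. That is a sponsor's judgement and no part of the conflict.

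**Conclusion.** The conflict is real, lies in the current operative text, and is confined to dosed subjects in the 6.2.1 monitoring-only group. Section 4.3 cites 5.2.1 alone, which leans towards withdrawal. But 6.2.1 also calls its three criteria withdrawal criteria, so the pointer does not decide the matter.

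For an affected subject the loss is 0 to 6 PK samples and 0 to 5 B-cell samples. With a last sample at Day 28, AUC(0-t) is biased low by about 27-32%, and log AUC(0-inf) carries an error SD of 0.06-0.18 against about 0.03 with full sampling. At trial level the effect is small: 22.0% to 22.1-22.3% for one such profile among 12. A reader might infer that the planned precision is in danger; the figures do not support that.

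These sizes rest on assumed settling times, A/B ratio and residual error. The documents give no rate for ALT 3 to <5xULN, so the expected number of affected subjects cannot be computed. This is a minor correction, worth making because it is cheap and because notification, work-up and monitoring for this group do not depend on withdrawal.

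**What to change.** - In 5.2.1 and Appendix 1 (and so in 4.3 by reference), state that after dosing, study withdrawal applies only to 6.2.1 criteria 1-3.
- State that a subject in the 6.2.1 monitoring-only group stays in the study for the scheduled PK, PD and safety visits to Day 84, with weekly liver monitoring added.
- Align the Table 4 liver-event form row for this group with Appendix 1, and check that the flow chart matches.
- Keep the 5.2.1 treatment stop for a result known before dosing. Leave notification, work-up and SAE reporting unchanged.

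Optional and separate, for the sponsor to decide: let dosed subjects who meet criteria 1-3 continue scheduled sampling where the investigator agrees, and add a PK and a B-cell sample to the Table 2 discontinuation column.

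Cost: a few sentences of protocol wording and a flow-chart check. Each affected subject continues with 0 to 6 visits that are already scheduled, and their blood draws.

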#### **Safety Follow-Up Procedures for subjects with ALT $\geq 3xULN$ :**

- Monitor subjects weekly until liver chemistries (ALT, AST, alkaline phosphatase, bilirubin) resolve, stabilize or return to within baseline values.

#### **Safety Follow-Up Procedures for subjects with ALT $\geq 3xULN$ and total bilirubin $\geq 2xULN$ (>35% direct bilirubin); or ALT $\geq 3xULN$ and INR^1 >1.5**

- This event is considered an SAE (see Section 7.1.3). Serum bilirubin fractionation should be performed if testing is available. If fractionation is unavailable, urinary bilirubin is to be measured via dipstick (a measurement of direct bilirubin, which would suggest liver injury).
- Make every reasonable attempt to have subjects return to the clinic within 24 hours for repeat liver chemistries, additional testing, and close monitoring (with specialist or hepatology consultation recommended).
- Monitor subjects twice weekly until liver chemistries (ALT, AST, alkaline phosphatase, bilirubin) resolve, stabilize or return to within baseline values.

**In addition, for all subjects with ALT  $\geq 3xULN$ , every attempt must be made to also obtain the following:**

- Viral hepatitis serology including:
  - Hepatitis A IgM antibody.

---

[figure not shown]
 INR testing not required per protocol and the threshold value does not apply to subjects receiving anticoagulants.

- Hepatitis B surface antigen and Hepatitis B Core Antibody (IgM).
- Hepatitis C RNA.
- Cytomegalovirus IgM antibody.
- Epstein-Barr viral capsid antigen IgM antibody (or if unavailable, obtain heterophile antibody or monospot testing).
- Hepatitis E IgM antibody.
- Blood sample for pharmacokinetic (PK) analysis, obtained as per the Time and Events Table (Table 2) of last dose. Record the date/time of the PK blood sample draw and the date/time of the last dose of study treatment prior to blood sample draw on the CRF. If the date or time of the last dose is unclear, provide the subject's best approximation. If the date/time of the last dose cannot be approximated OR a PK sample cannot be collected in the time period indicated above, **do not obtain a PK sample**. Instructions for sample handling and shipping are included in the SPM.
- Serum creatine phosphokinase (CPK) and lactate dehydrogenase (LDH).
- Fractionate bilirubin, if total bilirubin  $\geq 2xULN$ .
- Assess eosinophilia
- Record the appearance or worsening of clinical symptoms of hepatitis (fatigue, nausea, vomiting, right upper quadrant pain or tenderness, fever, rash or eosinophilia) on the AE CRF.
- Record use of concomitant medications, acetaminophen, herbal remedies, other over the counter medications, or putative hepatotoxins on the Concomitant Medications CRF.
- Record alcohol use on the Liver Events CRF.

The following are required for subjects with ALT  $\geq 3xULN$  **and** bilirubin  $\geq 2xULN$  ( $>35\%$  direct) but are optional for other abnormal liver chemistries:

- Anti-nuclear antibody, anti-smooth muscle antibody, and Type 1 anti-liver kidney microsomal antibodies, total IgG.
- Serum acetaminophen adduct high-performance liquid chromatography (HPLC) assay (quantifies potential acetaminophen contribution to liver injury in subjects with definite or likely acetaminophen use in the preceding week).
- Liver imaging (ultrasound, magnetic resonance, or computerized tomography) to evaluate liver disease.
- The Liver Imaging and/or Liver Biopsy CRFs are also to be completed if these tests are performed.

Refer to the diagram below for a visual presentation of the procedures listed above.

\*INR threshold does not apply to subjects receiving anticoagulants.

## 12.2. Appendix 2: American College of Rheumatology (ACR) Criteria for SLE

The ACR Criteria for the Classification of Systemic Lupus Erythematosus\* [Tan, 1982; Hochberg, 1997]

Criterion	Definition
1. Malar “butterfly” rash	Fixed erythema, flat or raised, over the malar eminences, tending to spare the nasolabial folds.
2. Discoid rash	Erythematous raised patches with adherent keratotic scaling and follicular plugging; atrophic scarring may occur in older lesions.
3. Photosensitivity	Skin rash as a result of unusual reaction to sunlight, by patient history or physician observation.
4. Oral ulcers	Oral or nasopharyngeal ulceration usually painless.
5. Arthritis	Nonerosive arthritis involving 2 or more peripheral joints characterized by tenderness.
6. Serositis	a. Pleuritis (convincing history or pleuritic pain or rub heard by physician or evidence of pleural effusion), OR b. Pericarditis (documented by ECG, rub, or evidence of pericardial effusion).
7. Renal disorder	a. Persistent proteinuria (>0.5 grams/day or >3 + if quantitation not performed) OR b. Cellular casts (may be red cell, hemoglobin, granular, tubular, or mixed).
8. Neurologic disorder	a. Seizures (in the absence of offending drugs or known metabolic derangements; ie, uremia, ketoacidosis, or electrolyte imbalance) OR b. Psychosis (in the absence of offending drugs or known metabolic derangements; ie, uremia, ketoacidosis, or electrolyte imbalance).
9. Hematologic disorder	a. Hemolytic anemia (with reticulocytosis) OR b. Leukopenia (<4000/Ml total on 2 or more occasions), OR c. Lymphopenia (<1500/Ml on 2 or more occasions), OR d. Thrombocytopenia (<100,000/Ml in the absence of offending drugs).
10. Immunologic disorder	a. Anti-DNA (antibody to native DNA in abnormal titer), OR b. Anti-Sm (presence of antibody to Sm nuclear antigen), OR c. Positive-finding of antiphospholipid antibodies based on 1) an abnormal serum level of IgG or IgM anticardiolipin antibodies, 2) a positive test result for lupus anticoagulant using a standard method, or 3) a false-

Criterion	Definition
	positive serologic test for syphilis known to be positive for at least 6 months and confirmed by Treponema pallidum immobilization (TPI) or fluorescent treponemal antibody (FTA) absorption test.
11. Antinuclear antibody (ANA)	Abnormal titer of ANA by immunofluorescence or an equivalent assay at any point in time and in the absence of drugs known to be associated with “drug-induced lupus” syndrome.

\* The proposed classification is based on 11 criteria. For the purpose of identifying patients in clinical studies, a person shall be said to have systemic lupus erythematosus if any 4 or more of the 11 criteria are present, serially or simultaneously, during any interval or observation.

